### Fixed tissue bank and serum bank

All 1000 patients randomised into the NEO-EXCEL trial will have primary core biopsies (taken prior to treatment) in order to provide material for diagnosis. Additional core biopsies will be taken for formalin fixation to provide material for the TRANS NEO-EXCEL research tissue bank. This will ensure that sufficient tissues, since core biopsies are not suitable for modifying into a tissue micro-array, will be available to test the hypotheses outlined below and those which may arise from the expression profiling described above.

In addition, we will retrieve tumour resection specimens to construct a tissue microarray in which to evaluate markers of clinical response identified by tissue expression profiling. Tissue will be collected at the central research laboratory (Endocrine Cancer Group) where material will be sectioned for further study/made into tissue microarrays.

The key hypothesis to be tested prospectively within TRANS NEO-EXCEL relates to the observed interaction between COX 2 and aromatase expression as a model to explain the efficacy of COX 2 inhibitors, such as celecoxib, in the treatment of invasive breast cancer. The product of the COX 2 enzyme, PGE2, induces expression of the transcription factors Snail/Slug which co-operatively modulate the I.3 promoter region of the aromatase gene. Paradoxically Snail/Slug are also closely involved in the regulation of E-Cadherin expression. Loss of E-Cadherin has been associated with increased tumour metastatic potential. Using paired pre/post treatment samples from TRANS NEO-EXCEL we will test the hypothesis that reduction of PGE2 production in breast cancer, via celecoxib treatment, reduces the metastatic potential by up-regulation of E-Cadherin expression. We will further test the hypothesis that down-regulation of Snail/Slug expression is linked both to alterations in E-Cadherin expression and to a reduction in aromatase expression (each of these markers will be measured by immunohistochemistry). There has been significant recent progress towards the identification of an appropriate antibody for aromatase analysis in paraffin embedded tissues (presented at the AROMATASE 2004 meeting in Edinburgh). We recognise however that this latter hypothesis may be also influenced

by the ability of aromatase inhibitors to initiate a positive feedback regulation pathway to increase aromatase expression. Thus we will explore both the relationship between changes within COX 2 treated and placebo treated tumours exposed to the two aromatase inhibitors selected for this trial. The secondary hypothesis which we will test in the context of NEO-EXCEL is that resistance to anastrozole, a competitive inhibitor of aromatase, may be related to up-regulation of aromatase, a mechanism which is less likely to impact exemestane, which is an enzyme poison.

It is likely that 10 sections will be available for most patients from the pre-treatment core biopsies. Using IHC ER, PgR, HER2 and COX 2 will be measured on all primary specimens. All subsequent results will be correlated with HER2 expression, COX 2 expression and also the degree of ER and PgR positivity (Allred scale) and any changes in these during aromatase inhibitor therapy. There will also be comparison with basic histology: nodal positivity, presence of LVI and grade of tumour as well as apoptosis (tunel assay) characteristics at the time of definitive surgery.

### **Serum response markers**

Whilst tumour markers may be of value in predicting early response (de novo resistance/sensitivity) we recognise the value of dynamic markers of response which, it is widely accepted, are likely to be those detected in the serum of patients with cancer. Both serum and plasma will be collected. We aim to utilise known and identify novel response markers for dynamic assessment of response in the serum of breast cancer patients collected at routine clinical assessment/treatment visits. Serum samples will be collected at baseline, 2 and 16 weeks. All patients will, as appropriate, have a sample at the time of surgery or relapse. Serum HER2/EGFr, CA125, CA15-3 and CRP will be assessed as each has been implicated in the monitoring of disease response in breast cancer. In addition we aim to use a novel approach, protein expression profiling ([www.raybio.com](http://www.raybio.com)), to simultaneously profile 64 cytokines in the serum of patients to prospectively identify potential novel markers of response. Markers which show significant expression levels in pre-treatment sera, and a significant decline post treatment, may provide useful candidate response markers.

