## 16. TRANSLATIONAL SCIENCE

Whilst there is extensive in vivo and in vitro data to suggest that inhibition of the COX 2 mediated synthesis of prostaglandins may promote tumour response and prevent tumour spread, there is no clear consensus as to the relevant mechanisms and their relative importance. Early experimental evidence suggests that prostaglandin E2 (PGE2) expression is elevated in breast cancer and that this is associated with tumour invasion. Prostaglandins are implicated in a wide range of molecular actions including: the induction of interleukin6 (IL-6) and other inflammatory cytokines, neo-vascularisation and tumour invasion/proliferation. The rationale for linking COX 2 inhibitors with aromatase inhibitors in endocrine-responsive disease is due to the action of PGE2, mediated via the 1.3 promoter of the aromatase gene itself and leading to enhanced aromatase expression as a direct consequence of COX 2 activity. Given the increasingly widespread use of celecoxib as a novel anti-tumour agent there is a strong need for a clearer understanding of the mechanisms by which COX 2 mediates its actions in vivo. NEO-EXCEL represents an ideal opportunity to investigate this question and to provide strong evidence for predictive factors that may be used to inform future treatment decisions.

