As a secondary objective, we intend to exploit the tissue collected by the NEO-EXCEL study to investigate expression profiles relating to tumour response to steroidal (exemestane) versus non-steroidal (anastrozole/letrozole) aromatase inhibitors. Patients with metastatic disease who have progressed after treatment with non-steroidal inhibitors (anastrozole and letrozole) have been treated with exemestane. Of 241 patients treated, 24% experienced clinical benefit (CR + PR + SD) lasting for a median time of 37 weeks. This suggests that there is a degree of non cross-resistance between these classes of aromatase inhibitors. Secondly, there appear to be differences between the molecular profiles of tumours responsive to steroidal irreversible (exemestane) and non-steroidal reversible inhibitors of aromatase, as suggested by data presented at the San Antonio breast cancer symposium^54. We therefore propose, within NEO-EXCEL, to establish a tissue and serum bank for future gene expression profiling and proteomic analysis to answer two key questions. Firstly and most importantly, we hypothesise the expression profiling of sequential tumour biopsies will identify molecular mechanisms which underpin the effects of the COX 2 inhibitor celecoxib in the context of neoadjuvant therapy of breast cancer. Secondly, we further hypothesise that markers of differential response to aromatase inhibitors will be identified in a linked analysis.

Our aim is to collect three sequential tumour samples (pre-treatment, 2 weeks after therapy initiation and at surgery) from patients randomised between the different aromatase inhibitors and also between celecoxib and placebo; these timepoints have been chosen to link to previous studies (Dixon et al, Dowsett et al) of early response to hormone therapy. We also aim to analyse, in a subset of patients (participating in the frozen tissue sub-protocol), sequential tumour biopsies and the changes in Gene Expression Profiles (GEPs) of breast tumours from each treatment arm to determine, at the level of gene expression, the molecular differences induced in tumours during treatment with exemestane and letrozole +/- celecoxib combination therapy. We predict that a number of the identified differentially expressed genes will serve as useful response markers for adjuvant studies (e.g. TEAM/ATAC). A significant change post treatment

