may provide useful candidate response markers in the context of neoadjuvant treatment, which may be profiled in the wider tumour databank (tissue microarrays) from the NEO-EXCEL trial.

It is now clear that only a small number of genes are up-regulated in all breast tumours. Furthermore, while single genetic markers in clinical specimens have often failed to be predictive of prognosis, recent studies have demonstrated that the GEP of multiple genes in combination can predict the response to tumours in terms of outcome and can provide prognostic and response information.

Affymetrix human GeneChip microarrays will be used to undertake this analysis, each containing oligonucleotides representing more than 39,000 transcripts derived from approximately 33,000 well-substantiated human genes. Such a set will include the majority of genes whose expression changes have been shown in the above studies to be relevant to the development or progression of different types of breast cancer. We propose to select 100 patients (50 patients from each treatment group) to yield 300 samples for expression array analysis. Our aim is to collect this material during the course of recruitment and to bank this material in a central laboratory prior to submission of a TRICC translational science project or CRUK project grant for the expression profiling of this material in conjunction with the CRUK Genome Profiling Laboratory at the Paterson Institute. Subsequently the predictive value of genes shown to be linked to tumour response from the study will be tested using material collected as formalin fixed tissue from the remainder (900 cases + 100 entered into the profiling sub-study). These profiles may also inform the analysis of samples in TRANS-REACT and TRANS-MA27.

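### The only stated criterion for a novel serum response marker is a fall after treatment, with no reference to clinical response or randomised arm

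*Protocol*

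**What the plan says.** The aim in Section 16, under Serum response markers, concerns response: "We aim to utilise known and identify novel response markers for dynamic assessment of response in the serum of breast cancer patients". The discovery tool is an array intended to "simultaneously profile 64 cytokines in the serum of patients to prospectively identify potential novel markers of response". On sampling: "Serum samples will be collected at baseline, 2 and 16 weeks".

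The only criterion given for a novel serum candidate is: "Markers which show significant expression levels in pre-treatment sera, and a significant decline post treatment, may provide useful candidate response markers". No later serum step relates the change to response or compares arms.

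The opening of Section 16 lists, among the actions in which prostaglandins are implicated, "the induction of interleukin6 (IL-6) and other inflammatory cytokines". Section 3.5 describes celecoxib as acting through inhibition of prostaglandin synthesis. Under Section 8.1 all four arms (1:1:1:1) contain an aromatase inhibitor and two contain celecoxib.

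Section 16 has a similar sentence for genes: "A significant change post treatment" "may provide useful candidate response markers in the context of neoadjuvant treatment". There, however, a further step follows: "Subsequently the predictive value of genes shown to be linked to tumour response from the study will be tested".

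**The concern.** A response marker has to behave differently in patients whose tumours respond and in those whose tumours do not. A before-and-after fall does not test that. With no untreated group, a fall may reflect the aromatase inhibitor, celecoxib, tumour shrinkage, or simply time. For cytokines the protocol itself supplies a direct drug route that needs no tumour response.

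Two errors follow if the criterion is applied as written. A cytokine suppressed by celecoxib in responders and non-responders alike qualifies as a candidate response marker. A marker that rises with response, or whose opposite movements in the two groups cancel, does not qualify. At stake is whether the serum sub-study labels pharmacodynamic markers as response markers and overlooks some real ones.

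**Working it through.** The protocol gives no test, significance level, sample size or effect size for the serum search, so there is no figure of its own to reproduce. The calculation below illustrates how the criterion behaves.

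**Inputs from the Protocol.** Response rate about 55% (Section 14.3, letrozole). Half the patients on celecoxib (Section 8.1). Panel of 64 cytokines (Section 16).

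**Assumed inputs.** Two-sided 5% tests; change from baseline with SD 1 within groups; drug shift 0.5 SD; responder/non-responder gap 0.6 SD; N = 100; all arms pooled for the decline test.

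**Rules compared.** (i) Decline: one-sample t test of the change, selected if significantly below zero. (ii) Response comparison: change regressed on response, adjusted for celecoxib, selected if the response term is significant in either direction. There were 3,000 simulated data sets per setting.

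| Marker (N = 100, 55% response) | Decline | Response comparison |
|---|---|---|
| A. Falls 0.5 SD with celecoxib only, unrelated to response | 66% | 5.2% |
| B. Falls 0.5 SD in everyone, unrelated to response | 99.9% | 4.5% |
| C. Gap of 0.6 SD by response, mean change zero | 2.1% | 84% |
| D. Rises 0.6 SD in responders only | 0% | 83% |

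**Check by hand** (critical t about 1.98):
- A, decline. Mean change = 0.5 × (−0.5) = −0.25. Pooled SD = √(1 + 0.25²) = 1.031. Selected if the mean is below −1.98 × 1.031/√100 = −0.204. The mean has standard error 0.1, so the probability is Φ((0.25 − 0.204)/0.1) = Φ(0.46) ≈ 0.68.
- C, response. Standard error of the gap = √(1/55 + 1/45) = 0.201. 0.6/0.201 = 2.99. Power ≈ Φ(2.99 − 1.98) = Φ(1.01) ≈ 0.84.
- C, decline. Responders change by −0.6 × 0.45 = −0.27 and non-responders by +0.6 × 0.55 = +0.33. The overall mean is 0.55 × (−0.27) + 0.45 × 0.33 = 0, so only the 2.5% lower-tail error remains.

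**Where the criterion does work.** A marker that falls 0.6 SD in responders and is flat in non-responders has mean change −0.33 and pooled SD √(1 + 0.36 × 0.55 × 0.45) = 1.044. It is selected with probability about Φ(3.3/1.044 − 1.98) = Φ(1.18) ≈ 0.88. The criterion finds such a marker but cannot tell it from A or B.

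**Sensitivity.** The pattern is the same for response rates of 45% to 65%. At N = 400 and 1,000 the decline rule selects A and B in at least 99.8% of runs, C in under 3% and D in none. The response comparison finds C and D in practically every run and selects A and B in 4.6% to 6.0%. A larger sample does not cure the problem.

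**Multiplicity.** If none of the 64 cytokines were related to response, uncorrected 5% comparisons would yield 64 × 0.05 = 3.2 false candidates on average. If independent, the chance of at least one is 1 − 0.95^64 = 96%. The replacement rule therefore needs error control.

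**The case against.** The sentence is hedged: it says such markers may be useful candidates. It names no test or analysis set and does not say that other markers are discarded. The work is exploratory, and marker analysis is often detailed in a separate plan. All of this is fair and limits the weight of the point. But the aim is stated in terms of response, and the one serum criterion written down does not match it. That is a criterion poorly chosen, not a detail left for later.

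A reader might infer three stronger things that the documents do not support.

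- **That the gene work has the same fault and spreads it.** The gene sentence is worded similarly, but Section 16 also studies expression profiles in relation to tumour response, compares changes across arms, tests genes linked to response in the fixed tissue, and uses the tissue microarray to evaluate markers of clinical response. Onward use in the tumour databank and in adjuvant studies is described for genes only; no serum marker is sent there.
- **That a direct celecoxib effect is almost certain to be selected.** The 99.9% in row B requires a fall in every patient. Only half receive celecoxib, and row A, at 66%, is the relevant figure for N = 100. That N is borrowed from the gene-array subset; no serum number is stated. Row C is deliberately the least favourable case for a decline rule.
- **That the whole serum panel is chosen this way.** CRP, CA15-3, CA125 and HER2/EGFr are also assayed, on the ground of an existing connection with response monitoring. The criterion bears on novel candidates, chiefly the 64 cytokines.

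**Conclusion.** The point holds for the serum criterion in Section 16. As written, it can admit cytokines lowered directly by treatment, and it does not admit markers that rise with response or whose movements cancel between responders and non-responders. Under the stated assumptions, a celecoxib-only effect unrelated to response is selected about 66% of the time against about 5% with an arm-adjusted response comparison. A response marker with zero mean change is selected about 2% against 84%. These percentages depend on assumed effect sizes, N and pooling of arms; the direction follows from the criterion itself.

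The gene sentence needs at most aligned wording. No primary or secondary outcome is affected.

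**What to change.** Replace the serum sentence in Section 16 with a definition along these lines:

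- A candidate serum response marker is one whose change from baseline to 2 weeks or to 16 weeks differs, in either direction, between patients with and without objective clinical response as defined in Section 14.1.
- The comparison is adjusted for celecoxib and aromatase inhibitor allocation, so that a drug that both lowers a cytokine and raises the response rate does not create the association.
- The false-discovery rate is controlled over the 64-cytokine panel, covering both time points if both are tested.
- The celecoxib-versus-placebo difference in change is reported separately, as a pharmacodynamic effect.

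Optionally, bring the gene sentence into line so that it refers to the response-linked step already planned.

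The cost is analysis wording only. The samples, assays, response assessments and allocations are already planned.

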## **17. SPONSORSHIP AND INDEMNITY**

This trial is a clinician-initiated and clinician-led study with a grant provided by Cancer Research UK and an educational grant from the pharmaceutical industry.

The Chief Investigator's NHS Trust hospital and the University of Birmingham will share responsibilities for co-sponsorship of the trial.

The trial is being coordinated by the Cancer Research UK Clinical Trials Unit at the University of Birmingham. These offices do not hold insurance against claims for compensation for injury caused by participation in a clinical trial and they cannot offer any indemnity. As this is a clinician-initiated study, ABPI guidelines for patient compensation by the pharmaceutical industry will not apply. There are no specific arrangements for compensation made in respect of any serious adverse events occurring through participation in the study, whether from the side effects listed, or others yet unforeseen.

In terms of liability, NHS Trust and Non-Trust Hospitals have a duty of care to patients treated, whether or not the patient is taking part in a clinical trial. Compensation is only available via NHS indemnity in the event of clinical negligence being proven.

## 18. PUBLICATION POLICY

The results of the analysis will be published in the name of the NEO-EXCEL trial in a peer reviewed journal, on behalf of all collaborators. All presentations and publications, including abstracts, relating to the main trial must be authorised by the NEO-EXCEL Steering Committee.

---

## Appendix 1: ECOG Performance Status

Status	Description
0	Asymptomatic, fully active and able to carry out all pre-disease performance without restriction.
1	Symptomatic, fully ambulatory but restricted in physically strenuous activity and able to carry out performance of a light or sedentary nature e.g. light housework, office work.
2	Symptomatic, ambulatory and capable of all self-care but unable to carry out any work activities. Up and about more than 50% of waking hours: in bed less than 50% of day.
3	Symptomatic, capable of only limited self-care, confined to bed or chair more than 50% of waking hours, but not bed-ridden.
4	Completely disabled. Cannot undertake any self-care. Totally bed-ridden.

---

## Appendix 2: Royal College of Pathologists Guidelines

National recommendations for assessment of steroid hormone positivity by immunostaining.

### Suggested scoring system

Score for proportion staining		Score for staining intensity	
0	No nuclear staining	0	No staining
1	<1% nuclei staining	1	Weak staining
2	1–10% nuclei staining	2	Moderate staining
3	11–33% nuclei staining	3	Strong staining
4	34–66% nuclei staining		
5	67–100% nuclei staining		

**Adding the two scores together gives a maximum score of 8.**

(*J Clin Pathol* 2000; 53:634-635)

## Appendix 3: Declaration of Helsinki

### Ethical Principles for Medical Research Involving Human Subjects

Adopted by the 18th WMA General Assembly Helsinki, Finland, June 1964  
and amended by the:

29th WMA General Assembly, Tokyo, Japan, October, 1975  
35th WMA General Assembly, Venice, Italy, October, 1983  
41st WMA General Assembly, Hong Kong, September, 1989  
48th WMA General Assembly, Somerset West, Republic of South Africa, October, 1996  
52nd WMA General Assembly, Edinburgh, Scotland, October, 2000

#### A. INTRODUCTION

1. The World Medical Association has developed the Declaration of Helsinki as a statement of ethical principles to provide guidance to physicians and other participants in medical research involving human subjects. Medical research involving human subjects includes research on identifiable human material or identifiable data.
2. It is the duty of the physician to promote and safeguard the health of the people. The physician's knowledge and conscience are dedicated to the fulfillment of this duty.
3. The Declaration of Geneva of the World Medical Association binds the physician with the words, "The health of my patient will be my first consideration," and the International Code of Medical Ethics declares that, "A physician shall act only in the patient's interest when providing medical care which might have the effect of weakening the physical and mental condition of the patient."
4. Medical progress is based on research which ultimately must rest in part on experimentation involving human subjects.
5. In medical research on human subjects, considerations related to the well-being of the human subject should take precedence over the interests of science and society.
6. The primary purpose of medical research involving human subjects is to improve prophylactic, diagnostic and therapeutic procedures and the understanding of the aetiology and pathogenesis of disease. Even the best proven prophylactic, diagnostic, and therapeutic methods must continuously be challenged through research for their effectiveness, efficiency, accessibility and quality.
7. In current medical practice and in medical research, most prophylactic, diagnostic and therapeutic procedures involve risks and burdens.
8. Medical research is subject to ethical standards that promote respect for all human beings and protect their health and rights. Some research populations are vulnerable and need special protection. The particular needs of the economically and medically disadvantaged must be recognized. Special attention is also required for those who cannot give or refuse consent for themselves, for those who may be subject to giving consent under duress, for those who will not benefit personally from the research and for those for whom the research is combined with care.
9. Research Investigators should be aware of the ethical, legal and regulatory requirements for research on human subjects in their own countries as well as applicable international requirements. No national ethical, legal or regulatory requirement should be allowed to reduce or eliminate any of the protections for human subjects set forth in this Declaration.

